4.4. Treatment Duration

The **start of the study** is defined as the date when the first patient in the whole study signs informed consent.

The **end of the study** is defined as the date of the last visit (including all follow-up visits) of the last patient in the whole study.

Patients will be evaluated for toxicities through AE reporting (continuously) and other safety assessments, weekly for the first 2 cycles during Part A and at the start of each 2 subsequent cycles thereafter. During Part B, patient's toxicities will be evaluated through AE reporting (continuous) and other safety assessments, weekly for the first 2 cycles and then at the start of each cycle for the first 4 cycles and every other cycle thereafter. Restaging will occur with imaging, laboratory chemistries, and tumor markers as defined in the Schedule of Assessments ([Table 1](#) and [Table 3](#)). Patients will continue on treatment until progressive disease (PD) as defined in Section [7](#) or intolerance of side effects. Patients who are receiving clinical benefit in the opinion of the treating Investigator may be allowed to stay on study after consultation with the Medical Monitor (Section [3.3](#)).

4.5. Concomitant Medications

Patients will be asked about prior medications during screening and instructed not to take any additional medications during the course of the study without prior consultation with the study team. At each visit, the patient will be asked about any new medications he or she is taking or has taken from 14 days prior to receiving their first dose of study drug until the 30-Day Safety Follow-up visit. Additionally, for the Safety Expansion portion of Part A and Part B, first subsequent anticancer therapy, will be collected as part of PFS/overall survival (OS), from the 30-day Safety Follow-up visit, and will be obtained every 3 months (± 14 days) until 2 years after the first study drug dose, death, loss to follow-up, withdrawal of consent, or end of the whole trial.

4.5.1. Permitted Concomitant Medications

Medications may be administered for maintenance of existing conditions prior to study enrollment or for a new condition that develops while on study, including but not limited to the following:

- Bisphosphonate use or receptor activator of nuclear factor kappa-B (RANK) ligand inhibitors, as recommended according to practice guidelines.
- Oral contraceptives.
- Hormone-replacement therapy.
- Megestrol acetate administered as an appetite stimulant.
- Transfusion of blood or red blood cells and/or prophylactic erythropoietin is permitted for the treatment of anemia (transfusion of blood or red blood cells is permitted from C1D1 until the EOT visit [see Section [3.2](#) Exclusion Criteria #11]).
- Transfusion of platelets is permitted from C2D1 until the EOT visit for the treatment of thrombocytopenia.
- Patients may take low-dose warfarin or a Coumadin preparation for maintenance of an open port.
- Concomitant use of corticosteroids at doses up to 10 mg prednisone or equivalent for the treatment of inflammatory conditions that are not prohibited by the applicable exclusion criteria is permitted.

- Prophylactic anti-emetics and anti-diarrheals are allowed for nausea and/or vomiting and diarrhea, per Institutional standards.

Supportive care and other medications considered necessary for the patient's safety and wellbeing may be given at the discretion of the Investigator, with the exception of those listed in Section 4.5.2.

4.5.2. Prohibited Concomitant Medications

The following treatments are prohibited while in this study:

- No other investigational therapy should be given to patients. No anticancer agents other than the study treatment should be given to patients from ≤ 14 days prior to the first dose of BDTX-189 for standard chemotherapy and from ≤ 28 days or 5 half-lives, whichever is shorter, for investigational drugs until 30 days after the last dose of BDTX-189. If such agents are required for a patient, then the patient must first be withdrawn from the study.
- No routine pre-medications will be given during the DLT evaluation period (Day 1 to Day 21 in Cycle 1 [Part A]), however, based on emerging clinical experience in earlier cohorts/patients, prophylactic administration of medications may be permitted at the discretion of the Investigator.
- Concomitant treatment with any medication that is known to prolong the QT interval and/or cause Torsades de pointes is prohibited from 14 days before the start of treatment until the EOT visit (see [Appendix F](#)). After study enrollment, if a patient requires use of any of these medications, the patient must be removed from study.
- Drugs known to be strong CYP3A4 inhibitors or inducers are prohibited from ≤ 14 days before the start of treatment until the permanent discontinuation of treatment. Refer to [Appendix E](#) for a comprehensive list of agents in these categories. These agents include, but are not limited to:
 - CYP3A4 inhibitors: azole antifungals (ketoconazole, voriconazole and itraconazole), macrolide antibiotics (clarithromycin, erythromycin), HIV protease inhibitors (indinavir and ritonavir), cimetidine, aprepitant, nelfinavir, nefazodone, and double-strength grapefruit juice.
 - CYP3A4 inducers: phenytoin, barbiturates, and rifampicin.
- Herbal preparations/medications known to be potent inducers of CYP3A4 are not allowed from ≤ 14 days before the start of treatment until permanent discontinuation of treatment. These herbal medications include, but are not limited to, St. John's wort, kava, ephedra (ma huang), ginkgo biloba, dehydroepiandrosterone (DHEA), yohimbe, saw palmetto, and ginseng.
- Proton pump inhibitors are prohibited from 1 week prior to the start of treatment until the discontinuation of treatment. If the reduction of gastric acidity is essential before or during the study at the Investigator's discretion, the patients may use H₂-receptor antagonists or antacids (this will **not** be allowed for patients participating in the Food-Effect Cohort from 1 week prior to the Day -4 dose until C1D1 [Section 5.3.1]). If applicable, these agents should be taken at least 8 hours before or 2 hours after the daily dose of BDTX-189.

Some prohibited medications may be allowed at the Investigator's discretion after approval by the Medical Monitor when the patient has unmet medical need to continue receiving such prohibited medication(s), no suitable alternative treatments are available, and the benefit-risk ratio is acceptable in the Investigator's opinion. This exemption may not be applied to other anti-cancer therapies or other investigational therapies.

4.5.3. Concomitant Medications to be Used with Caution

The following treatments should be used with caution while in this study:

- Sensitive substrates of BCRP (e.g., rosuvastatin, sulfasalazine).
- Strong inhibitors of P-gp (e.g., itraconazole, ritonavir) and BCRP (e.g., curcumin, cyclosporine A, eltrombopag).

A detailed list can be found at: <https://www.fda.gov/drugs/drug-interactions-labeling/drug-development-and-drug-interactions-table-substrates-inhibitors-and-inducers#table5-1>.

5. STUDY ASSESSMENTS AND EVALUATIONS

5.1. Overview

All patients should visit the study center on the days specified within this protocol. **The C1D1 visit will determine the visit calendar for the study, and all projected visits will be based on the C1D1 visit date.** Study visits must occur according to the study visit schedule and within the allowed protocol windows. Missed doses or dose interruptions should not alter the patient's study visit schedule. The complete Schedule of Assessments for this study is presented at the beginning of this protocol (see [Table 1](#), [Table 2](#), and [Table 3](#)). The key procedures required in this study include:

- Reporting of all AEs occurring after the ICF has been signed.
- Safety hematology, chemistry, coagulation, and PK samples throughout the study.
- Baseline and on-treatment blood biomarker assessments.
- Archived tumor samples or new pretreatment tumor biopsy.
- Baseline and on-treatment tumor biopsy, if tumor amenable by biopsy (Part A).
- Tumor assessments (based on computed tomography [CT], positron emission tomography [PET], and/or magnetic resonance imaging [MRI] scan) according to RECIST Version 1.1 (see [Appendix B](#)).
- ECG measurements (including ECGs time-matched to coincide with detailed PK assessments beginning with dose level 4 [200 mg QD]) at baseline and onwards.
- Cardiac function echocardiography (ECHO) or multigated acquisition scan (MUGA).

A cycle of treatment is scheduled to last 3 weeks (21 calendar days). Multiple procedures may be scheduled at the same time point relative to BDTX-189 dosing. Priority should be given to PK collection at the time specified. Vital signs and ECG assessments should be performed prior to specimen collections (except where ECG assessments are to coincide with PK sample collection).

5.2. Screening

At enrollment, each potential patient will provide written informed consent ≤ 28 days prior to initiation of treatment and prior to starting any study-specific procedures. Upon signature of the ICF, patients will be assigned a unique patient number as enrollment (screening) occurs.

The screening assessments described in the Schedule of Assessments ([Table 1](#), [Table 2](#), and [Table 3](#)) will be collected, reviewed, and determined to be acceptable by the site Principal Investigator or designee after obtaining informed consent prior to the initiation of treatment.

The following screening parameters should be recorded prior to initiation of treatment:

- Medical history and demographics.
- Physical examination (including height and weight).
- ECOG performance status ([Appendix A](#)).

- Vital signs (heart rate, systolic and diastolic blood pressure [BP], pulse oximetry, and oral or axillary temperature) and weight.
- ECG.
- Cardiac MUGA/ECHO (within 28 days; however, no need to repeat during the screening if a comparable assessment has been performed \leq 6 weeks from the date of consent).
- Hematology assessments (complete blood count [CBC] with hemoglobin, red blood cell count, total WBC count with ANC, absolute lymphocyte count, 5-part differential [% neutrophils, % lymphocytes, % or absolute value of: monocytes, basophils, eosinophils] and platelet count).
- Biochemistry assessments (sodium, potassium, chloride, bicarbonate, blood urea nitrogen (BUN) or blood urea, creatinine, calcium, albumin, total protein, AST, ALT, alkaline phosphatase [ALP], total and direct bilirubin, lactate dehydrogenase, amylase, lipase, magnesium, phosphorous, and glucose).
- Coagulation assessments (prothrombin time [PT], activated partial thromboplastin time [aPTT], and international normalized ratio [INR]).
- Urinalysis (protein, glucose, ketones, urobilinogen, occult blood, and microscopic sediment evaluation).
- Screening pregnancy test for WOCBP (serum).
- Baseline fresh tumor biopsy (or within 28 days prior to C1D1), if tumor is amenable for biopsy from dose level 5 (Part A).
- Archived or new tumor tissue sample (within 28 days if new tumor tissue sample) for patients in Part B and only for patients with allosteric *ErbB* mutations who have archival tissue in Part A.
- CT or MRI for tumor assessment.
- Genomic results
 - Part A: eligible genomic alteration and allosteric mutation and all co-occurring genomic alterations based on NGS testing.
 - Part B: some clinical sites do not routinely perform broad NGS testing of tumor tissue. These sites may need to prescreen some patients for eligible mutations which will require separate Sponsor approval and patient consent.

If the following assessments are performed within the prior 7 days and as part of the screening assessments, they do not need to be repeated pre-dose on C1D1: weight, ECOG performance status, hematology, clinical chemistry, coagulation, and urinalysis.

Tumor assessments (scans) should be performed \leq 28 days prior to initiation of treatment.

Relevant concomitant diagnoses and/or therapies present at study entry and/or during screening that are relevant to the patient's safety during the study as judged by the Investigator will be recorded in the eCRF (see Section 4.5 for details on concomitant medications).

5.3. Assessments During Study Treatment

Patients will remain on treatment as long as, in the opinion of the Investigator, they are deriving benefit and the criteria listed in Section 5.5 are not met. Please refer to the Schedule of Assessments (Table 1, Table 2, and Table 3) for detailed outlines of each visit during the treatment period for each part of the study.

5.3.1. Food-effect Assessment (Dose Escalation Part A)

The effect of food on the PK of BDTX-189 will be assessed in a single dose, fed/fasted randomized crossover design. Based on the projected exposures at the various dose levels, Food Effect evaluation is planned at dose level 5 (400 mg QD). Randomization will be performed by Development Innovations at the time of patient registration. The Food Effect evaluation will be executed without disruption of the Dose Escalation and DLT evaluation to the extent feasible. Dose level 5 (400 mg QD) will therefore proceed as described in Section 4.3.1 in patients not having Food Effect assessed. Assignment of 3 or more patients to dose level 5 (400 mg QD) for DLT assessment will take place according to Section 4.3.2.

Patients (n = up to 8 per meal type) will be assigned to the Food Effect evaluation as described below. Depending on emerging data, additional patients may be enrolled to meet the requirements of a pivotal Food Effect study. The SRC will decide how to allocate patients but should prioritize assignment of patients for DLT evaluation. Patients evaluated for Food Effect will not be counted in the Boin decision rule. Should any DLT occur in the Food-effect Cohort, this will not be included in the dose escalation/de-escalation rules in Table 6, but the SRC will take the information into account for the dose increment/decrement decisions. Once the Day -1 assessments are complete, the patients may continue study drug administration on C1D1. The dose will be 400 mg QD unless that dose level has been declared tolerated, and a decision made to escalate to dose level 6 (800 mg QD), in which case patients will be assigned to that dose level. Patients included in the Food Effect evaluation will not have additional PK samples collected on C1D1.

Patients will receive BDTX-189 as a single oral dose on Day -4 after fasting for at least 10 hours before dosing or immediately after consuming a high-fat breakfast. Patients will receive BDTX-189 in the opposite prandial state on Day -1. BDTX-189 will be administered QD in 21-day cycles starting on C1D1. On the assigned day of PK assessment in the fed state, 30 minutes prior to the planned BDTX-189 administration time, patients will be instructed to consume a high-fat meal (see below for an example breakfast) and must finish the meal within 30 minutes. Patients will be instructed to take their dose of BDTX-189 with approximately 240 mL water within 30 minutes after starting the high-fat meal. On the assigned day of PK assessment in the fasted state, BDTX-189 will be administered together with approximately 240 mL water, following an overnight fast of at least 10 hours. Patients should not consume any food for at least 4 hours after the dose. The use of agents that suppress gastric acidity (H2 receptor antagonists, proton pump inhibitors, and intraluminal antacids) and agents that delay gastric emptying are prohibited from 1 week prior to the Day -4 dose until C1D1, when only proton pump inhibitors will be prohibited, as described in Section 4.5.2. Please see Table 11 (PK Sample Collection Food Effect Part A) for specific time points.

Patients will be given a high-fat breakfast in order to assess food effects on the PK of BDTX-189. An example high-fat breakfast that will be provided is a standard McDonald's

breakfast, which might include an Egg McMuffin, bacon, hash browns, and milk. Note: Alternative food components/quantity and/or time (i.e., lunch) may be allowed as per timing of dose administration and as approved by the Investigator/Sponsor. In addition, a low-fat breakfast may also be assessed as emerging data dictate. An example low-fat breakfast may include 8 ounces of milk (1% fat), one boiled egg, and one packet flavored instant oatmeal with water (approximately 400-500 calories).

5.3.2. *Electrocardiogram Measurements*

Single ECGs will be required pre-dose at the time points indicated in the Schedule of Assessments ([Table 1](#), [Table 2](#), and [Table 3](#)). Electrocardiograms (single) will be obtained after the patient has been resting quietly in semi-supine position for at least 5 minutes before the ECG. Electrocardiogram parameters (PR interval, QRS interval, QTcF, and heart rate) will be recorded. When multiple assessments coincide, ECGs will be done immediately before the scheduled PK sample or any other blood draw.

Time-matched triplicate ECG measurements will also be collected for patients in Part A's Dose Escalation and Food-Effect cohorts, and patients who are undergoing detailed PK assessment of a smaller and reformulated tablet in the Safety Expansion. ECG measurements will coincide with the detailed PK assessments around the projected C_{max} in patients to evaluate any corrected QT (QTc) concentration-effect relationship. These ECG measurements will be performed in triplicate pre-dose and at 1.0, 2.0, 3.0, and 4.0 hours post-dose on C1D1 and C1D15 starting with dose level 4 (200 mg) and onwards for the QD schedule and starting with dose level 1 for the BID dosing schedule, if a more frequent dosing schedule is pursued. For each set of triplicate ECGs, three standard resting 12-lead ECGs will be obtained in close succession and not more than 2 minutes apart (4 minutes total for 3 ECGs). Electrocardiograms will be obtained after the patient has been resting quietly in semi-supine position for at least 5 minutes, prior to the first ECG procedure and during the triplicate ECG collection.

Please refer to the Schedule of Assessments ([Table 1](#) and [Table 2](#)).

5.3.3. *Response Assessments*

Patients will be evaluated for response to treatment after 2 cycles of treatment. Response will be assessed at 6-week intervals (± 3 days) during the first 24 weeks (8 cycles) of study treatment. Thereafter, patients will be evaluated for response to treatment every 12 weeks (± 7 days), at the EOT visit (if not performed within the previous 4 weeks), and at the discretion of the Investigator. Patients with PD or unacceptable toxicity should be discontinued from the study; patients with SD or response to therapy will continue treatment. However, patients who are receiving clinical benefit in the opinion of the treating Investigator may be allowed to stay on study beyond initial radiological progression after consultation with the Medical Monitor if it is felt that it is in the patient's best interest. The assessments to be performed at this time are specified in [Appendix B](#). All target and non-target lesions documented at screening must be assessed. Please refer to Section [7](#) for further instructions on evaluating response (e.g., PD, SD).

The following assessments will be performed if abnormal at baseline or if clinically indicated:

- CT scan or MRI of chest, abdomen, and pelvis plus any other sites of known disease.
- CT scan head/MRI brain if history of CNS metastasis.

Investigators must ensure that images of all chest and abdomen CT/MRI scans for patients enrolled in Part B are available for transmission to the Sponsor for a future central reading by a BICR committee depending on preliminary efficacy results from Part A (see separate imaging charter).

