^k Approximately 12-24 patients receiving the smaller and reformulated 200 mg tablet will have blood drawn at C1D1 and C1D15 to evaluate QTc exposure effects. These patients will undergo **additional triplicate ECGs (time-matched to coincide with detailed PK assessments)** will be obtained at C1D1 and C1D15 pre-dose and 1.0, 2.0, 3.0, and 4.0 hours (± 5 minutes) post-dose to evaluate QTc exposure effects. For each time point, three standard resting 12-lead ECGs will be obtained in close succession and not more than 2 minutes apart (i.e., 4 minutes total for 3 ECGs). ECGs will be obtained after the patient has been resting quietly in semi-supine position for at least 5 minutes before the first ECG and during the triplicate. On the PK collection day, patients should be instructed to wait until they arrive at the study center and receive instructions from study staff prior to taking their dose of study medication. Refer to Section [5.6](#) for further details.

^l MUGA or ECHO should be performed at Screening (if not performed ≤ 6 weeks prior to patient signing informed consent), ≤ 7 days before dosing on C4D1, C7D1, C13D1, EOT, and as clinically indicated. ECHO/MUGA may occur prior to signing of the ICF if completed at the clinical site as part of standard of care and performed in compliance with the protocol requirements.

^m Hematology will include CBC with hemoglobin, red blood cell count, total white blood cell count with ANC, absolute lymphocyte count, and 5-part differential [% neutrophils, % lymphocytes, % or absolute value of: monocytes, basophils, eosinophils] and platelet count. The Investigator (or designee) is responsible for reviewing available lab results for each patient prior to their first dose to ensure that there are no lab abnormalities or values worsening from screening that are clinically significant.

ⁿ Clinical chemistry (± 2 days) will include sodium, potassium, chloride, bicarbonate, BUN or blood urea, creatinine, glucose, bilirubin (total and direct), AST, ALT, LDH, alkaline phosphatase, amylase, lipase, calcium, magnesium, phosphorous, albumin, and total protein.

^o Urinalysis will include protein, glucose, ketones, urobilinogen, occult blood, and microscopic sediment evaluation. A 24-hour urine collection for assessment of urine protein will be performed whenever the urinalysis reveals $\geq 3+$ protein.

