Preliminary PK data available for 43 patients showed oral absorption was generally rapid. In the multiple patient cohorts, there were dose-dependent increases in exposure (i.e., maximum concentration [C_{max}] and area under the plasma concentration-time curve [AUC]) seen with single (C1D1) and multiple (C1D15) daily administrations up to 800 mg, before an exposure plateau was reached at 1200 mg (see [Figure 8](#)). Exposures at 800 mg QD were approximately 1.5-fold lower than projected from preclinical data. The median elimination half-life ($t_{1/2}$) across all dose levels ranged from 2.2 to 5.9 hours, which is in line with preclinical projections of approximately 2 hours. No consistent trend of accumulation or decreasing exposures on multiple dosing was indicated. In the ongoing Food Effect cohorts, evaluating the effect of a high-fat or

low-fat meal on the PK of BDTX-189, 6 patients are considered evaluable in each cohort. The effect of a high-fat meal on the PK of BDTX-189 suggests a slightly positive effect of food with geometric mean ratio for C_{max} and AUC_{0-t} of 1.0 and 2.3 respectively. Administration of BDTX-189 with food resulted in an approximately 2.5-fold increase in median t_{max} (median t_{max} 1.5 hours fasted, 3.5 hours low-fat meal, 4.0 hours high-fat meal) relative to administration in the fasted state, and no change in median $t_{1/2}$.

Based on the results described above, the Safety Review Committee (SRC) recommended that the remaining patients to be enrolled will be administered BDTX-189 following consumption of a meal (i.e., NF).

Figure 8 Relationship Between BDTX-189 Dose (mg/day QD) and Exposure (C_{max} and AUC_{0-t})

AUC_{0-t} =area under the plasma concentration-time curve from time 0 to the time of the last measurable concentration;
 C_{max} =maximum concentration.

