c ECG measurements will be performed in triplicate pre-dose and at 1.0, 2.0, 3.0, and 4.0 hours (+/- 5 minutes) post-dose on C1D1 and C1D15 starting with dose level 4 (200 mg) and onwards for the QD schedule and starting with dose level 1 for the BID dosing schedule. For each set of triplicate ECGs, 3 standard resting 12-lead ECGs will be obtained in close succession and not more than 2 minutes apart (4 minutes total for 3 ECGs); see Section [5.3.2](#).

d Patients on the BID schedule should have their 8-hour PK samples drawn prior to the second dose of the day.

e The 24-hour sample will be collected prior to the administration of study drug on Day 2 or Day 16, as appropriate.

In Part A, time-matched ECG measurements will be collected coinciding with the detailed PK assessments around the projected C_{max} in patients to evaluate any QTc concentration-effect relationship. See [Table 1](#), [Table 2](#), and Section [5.3.2](#) for specific time points.

For Part B, sparse PK blood samples will be collected at approximately the following time points:

- Cycles 1 to 5 and every other cycle thereafter (± 2 days), Day 1: One pre-dose, two post-dose blood draws, the 1st draw at 0.5 – 1.5 hours post-dose and the 2nd draw at 2 – 4 hours post-dose.

Note: An ad hoc PK sample should be drawn (whenever possible) in case of a severe adverse event or at pre-dose in the event of dose modification, to assess the safety of the patient.

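### The time-matched ECG grid still ends at 4 h after the move to non-fasting dosing; if the protocol's fed median Tmax of 3.5 to 4.0 h carries over, peak QTc coverage is thin and post-peak coverage nearly absent

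*Combined protocol and SAP*

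**What the plan says.** Section 5.3.2 states the purpose: "ECG measurements will coincide with the detailed PK assessments around the projected" Cmax, so that any relation between concentration and QTc can be evaluated. The times on C1D1 and C1D15 are given there ("These ECG measurements will be performed in triplicate pre-dose and at 1.0, 2.0, 3.0, and 4.0 hours post-dose"). They recur in Table 1 footnote k, in Table 10 footnote c, and in Table 2 footnote k for about 12 to 24 Safety Expansion patients on the reformulated 200 mg tablet ("will be obtained at C1D1 and C1D15 pre-dose and 1.0, 2.0, 3.0, and 4.0 hours").

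Section 1.1.7 gives median Tmax as "1.5 hours fasted, 3.5 hours low-fat meal, 4.0 hours high-fat meal" and says that food "resulted in an approximately 2.5-fold increase in median" Tmax. On the data behind this it says that "6 patients are considered evaluable in each cohort". The high-fat to fasted geometric mean ratios for Cmax and AUC0-t are reported as "of 1.0 and 2.3 respectively".

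The Synopsis and Sections 4.3 and 6.1.2 place new Part A patients, the Safety Expansion and Part B on dosing with a meal. Table 10 continues PK sampling at 6, 8 and 24 h. No triplicate ECG is paired with those samples.

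**The concern.** The ECG grid fits fasted dosing. With a median Tmax of 1.5 h, one post-dose set precedes the typical peak and three follow it (2, 3 and 4 h). With a low-fat meal only the 4 h set follows the median peak, by half an hour. With a high-fat meal the last set falls on the median peak and none follows. The protocol gives no reason for keeping the grid.

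The Safety Expansion patients in Table 2 footnote k are there specifically to evaluate QTc exposure effects on the reformulated tablet taken with food, which is what Part B will use. Scheduled Part B ECGs are single and pre-dose unless a triplicate is clinically indicated (Table 3 footnote j). The Safety Expansion triplicates are therefore the main chance to see post-dose QTc under Part B conditions. A high-fat AUC ratio of 2.3 with a Cmax ratio of 1.0 also suggests that food prolongs exposure rather than raising the peak, which makes the hours after 4 h more informative.

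**Working it through.** **Inputs.** ECG times 1, 2, 3 and 4 h (Section 5.3.2). Median Tmax 1.5, 3.5 and 4.0 h, with 6 evaluable patients per meal (Section 1.1.7). Nominal food-effect PK times 0.5, 0.75, 1, 1.5, 2, 3, 4, 6 and 8 h (Table 11). Half-life 2.2 to 5.9 h (Section 1.1.7).

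**1. The protocol's own figure.** 3.5/1.5 = 2.33 and 4.0/1.5 = 2.67; their mean is 2.50. The stated fold increase of about 2.5 is reproduced.

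**2. What the medians imply.** With six patients, the median is the average of the third and fourth ordered values. On the Table 11 times only these pairs are possible:

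| Meal (median) | 3rd, 4th values (h) | Tmax at or after 4 h | Tmax strictly after 4 h |
|---|---|---|---|
| Low-fat (3.5 h) | 3, 4 | 3/6 | 0/6 to 2/6 |
| Low-fat (3.5 h) | 1, 6 | 3/6 | 3/6 |
| High-fat (4.0 h) | 4, 4 | 4/6 to 6/6 | 0/6 to 2/6 |
| High-fat (4.0 h) | 2, 6 | 3/6 | 3/6 |

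So half of the low-fat patients, and at least half of the high-fat patients, peak at or after the last ECG. The number peaking strictly after it could be anything from 0/6 to 3/6 for either meal.

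**3. Illustration with a spread.** The protocol gives no Tmax variability. Assume a lognormal Tmax with a CV of 20% to 60%. Then P(Tmax > 4 h) = 1 − Φ(ln(4/median)/σ), where σ² = ln(1 + CV²). This gives 0% to 4% at a median of 1.5 h, 25% to 41% at 3.5 h, and 50% at 4.0 h.

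**4. How close the best ECG-paired concentration comes to Cmax.** Assume a one-compartment oral profile, a half-life of 2.2 or 5.9 h, a Tmax CV of 30% or 50%, and an absorption lag of zero or half of Tmax. None of these apart from the half-life range comes from the protocol. The ranges below cover both fed medians and all combinations.

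| ECG times (h) | Mean share of Cmax captured | Patients below 80% of Cmax |
|---|---|---|
| 1, 2, 3, 4 (current) | 81% to 99% | 0% to 25% |
| 2, 3, 4, 6 (1 h set moved) | 94% to 99% | 0% to about 6% |
| 1, 2, 3, 4, 6, 8 | 97% to 99.5% | 0% to 2% |

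The poor results on the current grid come from the long-lag cases. With no lag it captures a mean of 96% to 99%, and about 5% of patients at most fall below 80%.

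**The case against.** A reader might infer that the QTc analysis misses Cmax. The documents do not support that. A patient who peaks at 4 h has an ECG at the peak, and step 2 shows the medians are compatible with nobody peaking later. A concentration-QTc analysis uses paired values and does not need each patient's exact peak. Cmax itself is measured by the 6 and 8 h samples. Fasted data also cover the peak: Section 1.1.7 counts 7 + 21 + 6 = 34 patients treated fasting at 400, 800 and 1200 mg, with a median Tmax inside the grid, and the high-fat Cmax ratio is 1.0 (at 400 mg only). All of this stands.

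A reader might also infer that every patient is now dosed fed, or that QT safety is left unguarded. Neither follows. Section 5.6 keeps initial escalation patients fasted for detailed PK. Section 6.1.2 has Food-Effect patients dosing on an empty stomach, which needs to be reconciled with Section 4.3. The protocol also reports no hERG inhibition up to 7.5 µM and no cardiovascular effect in dogs (Section 1.1.6), excludes patients with QTcF above 470 msec, restricts QT-prolonging drugs, and has QTcF action rules in Table 8.

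The Tmax medians are preliminary and come from few patients on a single 400 mg dose with test breakfasts. Tmax for the reformulated tablet at the current dose with a standard meal is not given.

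What survives is narrower: the fasted data cannot show a late or delayed effect under food on the reformulated tablet, and the present grid barely looks for one.

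**Conclusion.** The point holds as a weakness of coverage. After the change to non-fasting dosing the ECG grid no longer brackets the peak that the protocol itself reports. About half of fed patients would peak at or after the last ECG, so post-peak QTc observation is nearly absent in them. This assumes that the food-effect Tmax carries over to the current dose, meal and tablet. Most patients probably still have an ECG-paired concentration near Cmax, so the estimated concentration-QTc relation is not invalidated. The loss is in detecting a late or delayed effect in the 12 to 24 Safety Expansion patients and in non-fasting escalation cohorts, such as the 400 mg BID cohort that Section 1.1.7 describes as enrolling. Confidence is moderate, because the fed Tmax rests on 6 patients per meal and its spread is unknown.

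**What to change.** In Section 5.3.2, Table 1 footnote k, Table 2 footnote k and Table 10 footnote c, state that patients having detailed PK in the non-fasting state have triplicates pre-dose and at 2.0, 3.0, 4.0 and 6.0 h. Take the 6.0 h set immediately before the existing 6 h PK draw; that draw has a ±30 minute window against ±5 minutes for the ECGs, so tie the ECG to the draw. Keep the current grid for patients dosed fasted.

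The number of ECG sets does not change, and these patients already stay for the 6 and 8 h samples. For twice-daily dosing the 6 h set falls before the second dose, because Table 10 footnote d says: "Patients on the BID schedule should have their 8-hour PK samples drawn prior to the second dose of the day".

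Costs: the 1.0 h ECG is lost in fed patients; fed and fasted grids will differ in a pooled concentration-QTc analysis; and the change needs a protocol amendment under Section 12.1. If the early ECG is wanted, adding the 6.0 h set and keeping 1.0 h gives nearly the same coverage for one more set per visit.
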